#### 8.4 Multiple Comparisons and Multiplicity

This study was not powered to detect any effects relating to secondary endpoints. Therefore, the secondary analysis will involve descriptive statistics and thus there is no requirement to consider multiple comparisons in formal hypothesis testing for secondary endpoints.

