#### 2.2.2 Secondary Endpoints

Secondary endpoints include, but are not limited to:

- Levels of acute phase reactant CRP over 35 days follow-up
- Length of hospitalisation from baseline (days)
- Survival at Day35, mortality data collected from EPIC database for both HCs and randomised individuals
- White blood cell count over 7 days follow-up
- Neutrophil count over 7 days follow-up
- Lymphocyte count over 7 days follow-up
- Monocyte count over 7 days follow-up
- Eosinophil count over 7 days follow-up
- Basophil count over 7 days follow-up
- Procalcitonin over 7 days follow-up
- D-dimer count over 7 days follow-up
- Blood pressure over 7 days follow-up
- Pulse rate over 7 days follow-up
- Temperature over 7 days follow-up
- Respiratory rate over 7 days follow-up
- Time on Oxygen over 7 days follow-up
- Time on Oxygen over 35 days follow-up
- Proportion of individuals with Pneumonia over 7 days follow-up
- Ordinal score (WHO scoring tool) over 7 days follow-up (including randomized individuals only)
- Proportion of individuals on Mechanical Ventilation (MV) over 7 days follow-up
- Time on MV over 7 days follow-up
- Length of ICU stay (hours) over 7 days follow-up
- Proportion of individuals with Pneumonia over 35 days follow-up
- Proportion of individuals on Mechanical Ventilation (MV) over 35 days follow-up
- Time on MV over 35 days follow-up
- Length of ICU stay (hours) over 35 days follow-up

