### **2.3 Statistical Hypotheses**

The statistical hypotheses are defined in terms of a 'zero effect' i.e. no difference between the treatments; the null hypothesis. The subsequent analyses test these statements to determine how much evidence there is to support the null hypothesis. A small p-value can be interpreted as a small probability of observing the result we obtained if there really was no difference between treatments, hence leading to rejection of the null hypothesis.

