### 2.3.2 Secondary null hypotheses

• There is no difference in secondary endpoints between hospitalised COVID-19 positive individuals receiving BAC + dornase alfa and hospitalised COVID-19 positive individuals receiving BAC only.

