#### **Exploristics Limited**

#### **11.2 Secondary endpoint analyses**

This study was not powered to detect any effects relating to secondary endpoints. Therefore, the secondary analysis will involve descriptive statistics. In general, continuous data will be summarised using the number of individuals, mean (standard deviation), median (1st and 3rd quartiles), minimum and maximum, and categorical data will be represented as frequency counts (percentages).

A further comparison of the secondary endpoints will involve the appropriate general linear models.

For the following secondary endpoints, the same model will be fitted as for the primary endpoint, except with the dependent variable as the secondary endpoint, and adjusting for the baseline level of the secondary endpoint, as opposed to baseline CRP (baseline defined as the last measurement prior to randomisation, or the first measurement following Dexamethasone for HCs):

- Levels of acute phase reactant CRP over 35 days follow-up. The difference from the primary analysis model is that observations will be included up to 35 days after baseline. The treatment comparison will be at the mean follow-up time.
- White blood cell count over 7 days follow-up
- Neutrophil count over 7 days follow-up
- Lymphocyte count over 7 days follow-up
- Monocyte count over 7 days follow-up
- Eosinophil count over 7 days follow-up
- Basophil count over 7 days follow-up
- Procalcitonin over 7 days follow-up
- D-dimer count over 7 days follow-up
- Ordinal score (WHO scoring tool) over 7 days follow-up (using randomized individuals only)

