For the following secondary endpoints, a survival analysis will be conducted. The number of events by arm will be compared. The time to event data will be censored at 28 days post last dose (Day35) for the randomised participants and at 35 days after baseline, or the date of the last electronic record, whichever is earlier, for the historical control group. If median time-to-event times exist, the Kaplan-Meier method will be used to estimate the median time-to-event times and the associated 95% confidence intervals. The survival model will include treatment as a stratification variable and significance assessed using a log-rank test. A Cox proportional hazards model will be used to generate a hazard ratio and associated confidence intervals, adjusting for age, baseline CRP value (defined as the last CRP measurement prior to randomisation, or the first CRP following Dexamethasone for HCs) and treatment as a main effect. For the time to discharge from hospital analysis, data will be censored if the participant dies prior to discharge at the date of death.

- Survival at Day35
- Time to discharge from hospital from baseline (days) to Day 35

For the following secondary endpoint, a logistic regression model will be fitted, with age, gender, BMI baseline CRP value (defined as the last CRP measurement prior to randomisation, or the first CRP

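### SAP 8.4 waives multiplicity because secondary analyses are descriptive, but SAP 2.3 and 11.2 plan hypothesis tests and treatment-effect models for secondary endpoints

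*SAP*

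**What the plan says.** SAP 8.4 starts from the lack of power for secondary endpoints and concludes that "the secondary analysis will involve descriptive statistics and thus there is no requirement to consider multiple comparisons in formal hypothesis testing for secondary endpoints".

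Other parts of the SAP describe something else:

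- SAP 2.3 introduces the null hypotheses with "The subsequent analyses test these statements to determine how much evidence there is to support the null hypothesis" and explains how a small p-value leads to rejection. SAP 2.3.2 then states one for the secondary endpoints: "There is no difference in secondary endpoints between hospitalised COVID-19 positive individuals receiving BAC + dornase alfa", compared with best available care only.
- SAP 11.2 repeats the descriptive statement and then goes further: "A further comparison of the secondary endpoints will involve the appropriate general linear models".
- For ten endpoints in 11.2, "the same model will be fitted as for the primary endpoint, except with the dependent variable as the secondary endpoint". In 11.1 that model's reporting runs through a z-score to a two-sided p-value.
- For survival at Day 35 and time to discharge, 11.2 has "significance assessed using a log-rank test", alongside a Cox hazard ratio adjusted for age and baseline CRP.
- Nine further endpoints in 11.2 get logistic or linear models with a treatment term.
- Only six endpoints in 11.2 are restricted to summary statistics: blood pressure, pulse, temperature, respiratory rate, and time on mechanical ventilation to 7 and to 35 days.

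Protocol 11.3.3 also calls the secondary analysis descriptive and also adds models. It frames their output as adjusted means, group differences, hazard ratios and confidence intervals, and it contains no log-rank test and no significance wording for secondary endpoints.

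**The concern.** The waiver in 8.4 rests on a premise that 11.2 contradicts. Leaving secondary endpoints unadjusted is defensible if they are reported as estimates and nothing is declared significant. It is not defensible to skip adjustment because no testing takes place and then to assess significance. Lack of power does not rescue the argument, since low power does not lower the type I error rate.

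At stake is how a nominally significant result for survival, discharge, D-dimer or lymphocytes could be presented. The plan allows it to be called significant and also says that multiplicity need not be considered.

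Survival and discharge have a second problem. The log-rank comparison that decides significance takes no account of covariates, while the hazard ratio beside it does. The controls are mostly not randomised, so the two can point in different directions, and the SAP does not say which governs.

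**Working it through.** **The plan's own figure.** The documents give no familywise error rate for secondary endpoints. The only related figure is the 80% power of the primary comparison (SAP 5: control mean 99 mg/L, SD 62 mg/L, 40% relative difference, 30 active and 60 control).

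- Difference = 0.40 × 99 = 39.6 mg/L.
- Standard error = 62 × √(1/60 + 1/30) = 13.86.
- 39.6 / 13.86 = 2.86, which gives power of about 0.81 at two-sided 5% (0.807 with the t distribution).

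The stated 80% is reproduced, and nothing below alters it.

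**Count of modelled secondary endpoints (SAP 11.2).**

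- Mixed model as for the primary: 10 (CRP to 35 days, white cells, neutrophils, lymphocytes, monocytes, eosinophils, basophils, procalcitonin, D-dimer, WHO score).
- Log-rank and Cox: 2 (survival, time to discharge).
- Logistic: 4 (mechanical ventilation and pneumonia, each to 7 and 35 days).
- Linear: 5 (ICU stay and time on oxygen, each to 7 and 35 days; length of hospitalisation).

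Total 10 + 2 + 4 + 5 = 21. The supplementary logistic model for any ICU stay would add one or two and is left out.

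**How many of these are tests.** Two have an explicit significance test. If the p-value step of 11.1 carries over with the model, ten more have one, making 12. The nine logistic and linear models have no stated p-value or criterion.

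**Chance of at least one false positive.** The 5% level in SAP 11.1 is stated for the primary endpoint. Using 5% for each secondary test is an assumption, as is that all nulls are true. For k independent tests the chance is 1 − 0.95^k:

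- k = 2: 1 − 0.95² = 0.0975.
- k = 12: 1 − 0.95¹² = 0.46.
- k = 21: 1 − 0.95²¹ = 0.66, with 21 × 0.05 = 1.05 false positives expected.
- The chance first passes one half at k = 14 (0.51; k = 13 gives 0.49).

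The endpoints are not independent. The 7- and 35-day versions overlap, the white cell count contains its differentials, and length of hospitalisation nearly duplicates time to discharge. The documents give no correlations, so a range was simulated for 21 correlated normal test statistics (200,000 draws):

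| Assumed correlation | Chance of at least one |
|---|---|
| common, 0.1 | 0.64 |
| common, 0.3 | 0.55 |
| common, 0.5 | 0.43 |
| common, 0.7 | 0.29 |
| in blocks, weak | 0.60 |
| in blocks, strong | 0.39 |

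The block cases group white cell counts, inflammatory and coagulation markers, and clinical course, with higher correlation within near-duplicate pairs.

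**Share of non-randomised comparators.** SAP 11.2 uses the primary analysis population for secondary endpoints. SAP 12 plans 10 patients randomised to best available care and 60 matched historical controls, so 60 / 70 = 86% of comparators are historical. The WHO score is an exception, as it uses randomised patients only.

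**The case against.** The best defence is that the documents intend estimation. Both say the study was not powered for secondary endpoints, Protocol 11.3.3 describes intervals rather than tests, there is one declared primary test in a Phase IIa trial, and no secondary claim is planned. A fitted model is not a significance test. Whether secondary p-values will be tabulated depends on table shells that the SAP keeps in a separate file. Much of this stands, and it limits the size of the point. It does not answer the explicit log-rank wording or the hypothesis-testing language in 2.3 and 2.3.2. The six endpoints marked for summary statistics only also show that the authors meant the other 21 to go beyond description.

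A reader might infer that at least one false positive is more likely than not. The documents do not support that. It needs a 5% rule for every secondary endpoint, which is nowhere stated, all nulls true, and the equivalent of at least 14 independent tests. Nor does the log-rank test apply to all 21 models; it applies to two.

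A reader might also take "Secondary endpoints include, but are not limited to" in SAP 2.2.2 to mean that the number of comparisons is unlimited. SAP 11.2 lists the planned analyses endpoint by endpoint, so the point does not depend on closing that list.

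On the log-rank test, propensity matching in SAP 11 should reduce baseline imbalance, and how far the unadjusted and adjusted results might differ cannot be quantified from the documents. Matching need not remove all imbalance, however, and an adjusted estimate is already planned.

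**Conclusion.** The inconsistency is real: the reason given in SAP 8.4 does not fit 2.3, 2.3.2 and 11.2. Under an assumed 5% level per test and all nulls true, the chance of at least one false positive is at most about 66% for 21 independent tests, 46% for the 12 independent tests with an explicit or inherited p-value, and roughly 40-60% for 21 tests under plausible correlation. Uniformly high correlation would bring it lower (29% at 0.7). It is well above 5% in each of these cases, but not reliably above one half. These figures also assume that each test holds its nominal level, which confounding against historical controls could upset.

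Separately, significance for survival and time to discharge rests on an unadjusted test in a comparison where 86% of planned controls are historical. The primary endpoint's alpha, power and sample size are not touched. This should be corrected, but it does not undermine the trial's main analysis.

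**What to change.** Make 8.4 true and bring the SAP into line with Protocol 11.3.3:

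- Limit the hypothesis-testing text in SAP 2.3 to the primary endpoint and delete 2.3.2. Deleting 2.3.2 alone would leave the general testing statement in place.
- State in 11.2 that the z-score and p-value step of 11.1 does not apply to secondary endpoints.
- Delete the log-rank significance wording and take the survival and discharge effects from the adjusted Cox model already planned.
- Report all secondary effects as estimates with 95% confidence intervals, labelled exploratory and not adjusted for multiplicity, with no significance claims. The label matters, because an interval that excludes no effect carries the same chance of error as a 5% test.

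The cost is SAP wording and table shells; no new data or analyses are needed. The downside is that secondary endpoints will have no confirmatory p-values.

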#### 9. DATA HANDLING CONVENTIONS

#### 9.1 Premature Withdrawal and Missing Data

Mixed models will be used to analyse most endpoints; these models handle missing data naturally. Therefore, all available data will be included in all models.

#### 9.2 Derived and Transformed Data

Continuous endpoints will be assessed for conformance to normality and homogeneity of variance assumptions and the appropriate transformation will be conducted if necessary.

### **10. DESCRIPTIVE STATISTICS**

#### **10.1** Disposition of Subjects

Patient disposition will be listed. Summaries of the following patients will be presented:

- Number of individuals screened
- Number of individuals randomised
- Number of individuals who completed 7 days follow up, or follow-up to discharge from hospital, whichever occurred sooner.
- Number of individuals who withdrew consent or were lost to follow up
- Number of individuals who discontinued dornase alfa for any reason
- Number of individuals with protocol violations, to define PP population
- Number of matched historical controls or biobank samples included in the analysis

### **10.2 Demographic and Baseline Characteristics**

Baseline characteristics will be summarised by treatment (BAC + dornase alfa vs. BAC only) and by population: BAC + dornase alfa, randomised to BAC only, matched historical controls.

#### **Exploristics Limited**

### Identifier: EXP20012 Clinical Study Identifier: 132333

The following baseline characteristics will be presented:

- Age
- Gender
- Ethnicity
- BMI
- Baseline CRP (defined as the last CRP value prior to randomisation, or the first CRP following Dexamethasone for HCs)
- Whether they have a key comorbidity, defined as one or more of hypertension, diabetes or cardiovascular disease
- White blood cell count
- Neutrophil count
- Lymphocyte count
- Monocyte count
- Eosinophil count
- Basophil count
- Procalcitonin
- D-dimer count
- Ordinal score (WHO scoring tool), using randomized individuals only.
- Last Pre-Dexamethasone CRP (mg/L)
- Days between diagnosis and hospitalization
- Days between hospitalization and baseline
- Days between Dexamethasone initiation and baseline

#### 11. ANALYSIS CORRESPONDING TO THE STUDY OBJECTIVES

To identify individuals to include in the analysis from the historical controls cohort, the matching procedure will include an initial application of the study inclusion and exclusion criteria to identify the subjects that meet the criteria within the database. Further matching will involve the use of propensity scores to select the controls that most closely match with participants in the active treatment group. The propensity score model will be a logistic regression including all individuals randomised to dornase-alfa and all HCs, with an indicator variable as the outcome to indicate whether the individual is randomised or in the historical control cohort, and covariates included in the model for age, gender, BMI, baseline CRP (defined as the last CRP value prior to randomisation, or the first CRP following Dexamethasone for HCs), and whether they have a key comorbidity, defined as one or more of hypertension, diabetes or cardiovascular disease. The propensity matching will be done using a nearest neighbour approach.

Two controls will be matched for each participant in the active group.

As a supplementary analysis, the propensity score matching will be repeated, but instead of matching on baseline CRP as defined as the last CRP value prior to randomisation, or the first CRP following Dexamethasone for HCs, the matching will be done using the last pre-Dexamethasone CRP measurement, as well as the other factors defined above.

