11.3.2 Primary outcome analysis

The primary outcome analysis will involve the primary endpoint and the primary analysis population. The endpoint will be summarised overall, by treatment group and by day. Data will be summarised using the mean (standard deviation), median (1st and 3rd quartiles), minimum and maximum, and 95% confidence intervals.

The primary endpoint will be compared between groups using a repeated measures mixed model, adjusted for age, gender, BMI, baseline value, oxygen requirements, time from baseline, and the number of comorbidities and with treatment as the main effect and treatment by time as an interaction effect. Prior to analysis, the primary endpoint will be assessed for conformance to normality assumptions and the appropriate transformation will be conducted if necessary. This model-based approach is likely to be more robust to missing or spurious data. Treatment effect will be declared significant at the 5% level of significance.

The primary analysis population comprises the active treatment group and historical matched controls. The matching procedure will include an initial application of the study inclusion and exclusion criteria to identify the subjects that meet the criteria within the database. Further matching will involve the use of propensity scores to select the 60 controls that most closely match with participants in the active treatment group. The propensity score model will include age, gender, BMI, baseline CRP, oxygen requirements and the number of comorbidities and two controls will be matched for each participant in the active group.

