#### **Exploristics Limited**

# Identifier: EXP20012

Clinical Study Identifier: 132333

routinely measured and will be available in the database. Participants in the database will be selected to act as controls as follows:

- 1. Apply the inclusion and exclusion criteria of the COVASE study
- 2. Additional selection to identify closest matches using a propensity score based on age, gender, BMI, baseline CRP (defined as the last CRP value prior to randomisation, or the first CRP following Dexamethasone for HCs) and whether they have a key comorbidity, defined as one or more of hypertension, diabetes or cardiovascular disease (see Section 11 for details).

At least 60 control participants are expected to be available to act as controls.

Other ongoing and planned trials may be a source of cytokine data as well as biobanked samples that could be used to provide control information on the exploratory endpoints (e.g. ISARIC and RECOVERY Trials) assuming suitable consent is available.

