#### 8.2 Independent Variables

For the primary endpoint analysis, the independent variables included in the model will be treatment (dornase alfa vs. no dornase alfa), age, gender, BMI, baseline CRP level (defined as the last CRP value prior to randomisation, or the first CRP following Dexamethasone for HCs), time from baseline and whether they have a key comorbidity, defined as one or more of hypertension, diabetes or cardiovascular disease. An interaction term between treatment and time from baseline will also be included in the model.

For secondary endpoint analyses, the same covariates will be included in the models as for the primary endpoint analysis.

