#### **11.1 Primary endpoint analysis**

#### **Exploristics Limited**

### Identifier: EXP20012 Clinical Study Identifier: 132333

The primary endpoint will be compared between groups using a repeated measures mixed model, adjusted for age, gender, BMI, baseline CRP value (defined as the last CRP measurement prior to randomisation, or the first CRP following Dexamethasone for HCs), time from baseline, and whether they have a key comorbidity, defined as one or more of hypertension, diabetes or cardiovascular disease. An interaction between treatment and time from baseline will also be included in the model. CRP measurements more than 7 days after randomisation (or date of first CRP measurement following Dexamethasone initiation for HCs) will be removed from the analysis, so the comparison is over 7 days.

Due to the treatment by time interaction effect being included in the model, examining the treatment effect alone would be an inappropriate comparison, therefore the least squares means and 95% confidence intervals at the mean follow-up time will be compared between arms, which will take into account both the treatment effect and the treatment by time interaction. These means will be presented on the real scale, e.g. taking the antilog of the least squares mean if the dependent variable has been log-transformed. The difference between the least squares means (on the scale the model was fitted) and the standard error of the difference will be used to generate a treatment z-score, which will be compared against the normal distribution with mean 0 and variance 1, to obtain the two-sided p-value.

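### The SAP drops the protocol's oxygen-requirement covariate from matching, primary model and baseline list without a stated reason, leaving baseline oxygen need uncontrolled beyond eligibility in 60 of 70 primary controls

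*SAP*

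**What the plan says.** **Protocol.** Section 11.3.2 states: "The propensity score model will include age, gender, BMI, baseline CRP, oxygen requirements and the number of comorbidities". It specifies the primary analysis as a "repeated measures mixed model, adjusted for age, gender, BMI, baseline value, oxygen requirements, time from baseline, and the number of comorbidities". Section 5.1 (Study controls) gives the same matching list, and section 11.3.1 names oxygen requirements among the key baseline data for comparing groups.

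**SAP.** The matching model in section 11 has "covariates included in the model for age, gender, BMI, baseline CRP (defined as the last CRP value prior to randomisation", with key comorbidity completing the list. Section 3 (Study controls) agrees: "Additional selection to identify closest matches using a propensity score based on age, gender, BMI, baseline CRP (defined as the last CRP value". For the primary model, section 8.2 says "the independent variables included in the model will be treatment (dornase alfa vs. no dornase alfa), age, gender, BMI, baseline CRP level", followed by time and key comorbidity, and section 11.1 has "adjusted for age, gender, BMI, baseline CRP value (defined as the last CRP measurement prior to randomisation" with the same additions. The baseline list in section 10.2 has no oxygen item. Its one entry that could reflect respiratory support is "Ordinal score (WHO scoring tool), using randomized individuals only".

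**Audit trail.** Version 1.3 records the change from number of comorbidities to key comorbidity. Version 1.5 says ventilation and ventilator-associated pneumonia incidence could not be reliably inferred. Version 1.6 removes the by-day oxygen summary for lack of data, and removes historical controls from the WHO score analysis because they have no score. No entry mentions oxygen as a matching variable, model covariate or baseline item.

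**The concern.** The primary comparison sets 30 patients on dornase alfa against a pooled control group that is mostly historical. Its validity rests on matching and adjustment. The protocol treated oxygen need as important enough to name in both. It also gives grounds for a link with the outcome: section 5.1 describes relapse as CRP and oxygen requirement rising together.

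Eligibility covers part of the gap but not all of it. The inclusion criterion fixes the saturation reached on supplementary oxygen, not the flow or device needed to reach it. SAP section 5 applies the criteria to historical controls only where the data exist. Two eligible patients can therefore differ in oxygen need. If historical controls differ systematically from trial patients in this respect, the difference can pass into the treatment estimate, and no item in the SAP's baseline list would show it.

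**Working it through.** **1. Side by side**

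| Use | Protocol | SAP |
|---|---|---|
| Propensity score | oxygen included (5.1, 11.3.2) | absent (3, 11) |
| Primary model | oxygen included (11.3.2) | absent (8.2, 11.1) |
| Baseline comparison | oxygen included (11.3.1) | absent (10.2) |
| Reason for the change | n/a | none in audit trail |

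**2. The plan's own figure.** Inputs (SAP 5): control mean 99 mg/L, SD 62 mg/L, 40% relative difference, two-sided 5%, 30 active and 60 controls. The target is 0.40 × 99 = 39.6 mg/L. A two-sample t-test gives power 0.807, which reproduces the stated 80%. With the SAP's pooled controls (30 vs 70), power is 0.826 by t-test or 0.833 by normal approximation. The normal form is used in steps 4 and 6.

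**3. Share of controls.** SAP 12 plans 10 randomised and 60 historical controls: 60/70 = 85.7%. At the maximum size it is 72/84 = 85.7%. A shift of x mg/L in the historical controls biases the pooled contrast by 0.857x.

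**4. Illustrative size.** The documents give neither the oxygen gap nor its relation to CRP, so both are assumed. Let g be the gap in SD units, r the partial correlation of oxygen need with CRP, and rho the correlation of baseline CRP with the outcome.
- Residual SD: s = 62 × √(1 − rho²), which is 62.0 at rho 0 and 53.7 at rho 0.5.
- SE = s × √(1/30 + 1/70) = 13.53 or 11.72.
- Bias = r × g × s × 60/70.
- At g = 0.5, r = 0.3: 0.3 × 0.5 × 62.0 × 0.857 = 8.0 mg/L (20% of target), or 6.9 mg/L (17%) at rho 0.5. Type I error is 9.1% in both cases.
- If the bias hides the effect, power falls from 0.83 to 0.65, or from 0.92 to 0.80 at rho 0.5.
- Over g from 0.2 to 0.8 and r from 0.1 to 0.5, bias is 0.9 to 21.3 mg/L and type I error 5.1% to 35%. With r = 0.1, type I error never exceeds 6.1%.

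**5. Can the SAP's own checks detect it?** SAP 8.3.1 plans two relevant comparisons (t-test basis, rho 0 to 0.5).
- Dornase alfa vs randomised BAC, 30 vs 10: power for 39.6 mg/L is 0.40 to 0.50.
- Randomised BAC vs matched historical controls, 10 vs 60: at rho 0 the 95% CI half-width is 1.995 × 62 × √(1/10 + 1/60) = 42.3 mg/L; at rho 0.5 it is 36.6. At rho 0, power for a shift of 0.5 × 0.3 × 62 = 9.3 mg/L is about 7%.

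**6. Price of the covariate.** A 0.5-SD shift in historical controls is a 0.5 × 60/70 = 0.43 SD gap against pooled controls. Variance inflation is about 1 + 0.3 × 0.7 × 0.43² = 1.04, so power moves from 0.83 to 0.82. If historical controls without the value drop out, power at rho 0 is:
- 30% lost (52 controls left): 0.78
- 50% lost (40 left): 0.74
- 70% lost (28 left): 0.66

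These figures collapse repeated CRP values to one per patient. The mg/L values do not carry over if CRP is log-transformed.

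**The case against.** **Data may be the unstated reason.** The version 1.5 and 1.6 entries suggest that respiratory-support data in historical controls are weak. This stands as a warning about feasibility, but the entries concern other analyses. A reader might infer that the by-day oxygen entry explains the missing covariate; the text does not say so. SAP 11.2 still models time on oxygen in a population that includes historical controls, so some oxygen data are expected. That endpoint counts any oxygen regardless of amount, so flow may be sparse.

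**A respiratory covariate may be intended.** SAP 11.2 lists *serious condition* first in its order of covariate removal. In the protocol that phrase labels the respiratory exclusion (7.1.3). The SAP does not define it and includes it in no model list, so it cannot be counted as an oxygen adjustment. It does need clarifying.

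**Oxygen is reported elsewhere.** A reader might infer that oxygen is never tabulated for historical controls. That goes too far: time on oxygen is a secondary endpoint, and the separate tables file cited in SAP 13.1 is not available. The supportable statement is that no oxygen item is in the SAP's baseline list.

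**Deviations will be disclosed.** Protocol 11.5 promises that deviations will be described and justified in the final report. That would disclose the omission but not correct for it.

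**The bias may be negligible.** This stands. The inputs are assumptions, and the low end of the range is close to no effect.

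**Conclusion.** The discrepancy is certain: three uses of oxygen requirements in the protocol, none in the SAP's corresponding lists, and no reason logged. Beyond a partly applied eligibility screen, baseline oxygen need is uncontrolled in 60 of 70 primary controls, and about 86% of any resulting shift enters the primary estimate.

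The consequence is not certain. A reader might conclude that the primary result is biased, or biased in favour of dornase alfa. The documents support neither, because the oxygen gap, its correlation with CRP and its direction are unknown. What they do support is that the plan neither removes such a shift nor could reliably detect one: the within-control interval (37 to 42 mg/L either side) is about as wide as the target effect itself. This should be corrected, with high confidence in the textual finding and low confidence in any particular size of bias.

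**What to change.** 1. Before CRP outcomes are compared, count the eligible historical controls with a baseline oxygen value at the SAP's baseline time: flow, device, or at least any oxygen versus none.
2. Where data allow, restore that term to the primary model, the baseline table and the propensity score, as the protocol states. The model term matters most. SAP 3 says "At least 60 control participants are expected to be available to act as controls", and if only about 60 are eligible, choosing 60 of them leaves matching little room.
3. State how patients missing the value are handled. SAP 9.1 relies on mixed models, which do not cover missing covariates.
4. If too few have the value, keep the SAP model as primary, report the oxygen-adjusted model in those with data as a sensitivity analysis, and record the departure from the protocol with its reason.
5. Define or delete *serious condition* in SAP 11.2.

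**Cost:** SAP wording, one extraction from historical records, one model term and one table row. The statistical price is the small variance inflation in step 6 plus any loss of controls without the value. That loss could be substantial, given the audit-trail entries on data quality, which is why the count comes first.
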